8.2.5. Local Site Injection Tolerability Assessment (PF-06801591 only)

Any injection site reactions will be recorded as adverse events.

8.2.6. Survival Follow-up

To collect OS data for Cohort A participants only, once participants enter the survival follow-up period, they will be contacted by telephone every 12 weeks (± 7 days) until consent withdrawal, lost to follow-up, death, or end of the study (5 years after last participant randomized to Cohort A). If the participant is seen in the clinic during the window of time that a scheduled telephone call is to be made to collect survival data, then the clinic visit may replace the survival telephone call. For Cohort A participants only, any subsequent anti-cancer therapy (including cystectomy), if administered, will be documented and recorded for participants who discontinue the study intervention and continue in post-treatment safety follow-up until recurrence of high-grade disease or progression of disease. The sponsor may request that sites complete additional survival follow-up to facilitate planned analyses as needed.

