Based on preclinical and clinical data, an intervention in BCG-naïve participants with high-risk NMIBC, with PF-06801591 in combination with BCG induction therapy (with or without maintenance therapy) may provide a greater benefit with longer event-free survival and reduction in the rate of subsequent cystectomy as compared to SOC BCG treatment. In addition, PF-06801591 is administered subcutaneously (SC) every 4 weeks which is expected to reduce burden for the participants and for the healthcare system.

Rationale for Cohorts B1 and B2

BCG treatment fails in approximately 40% of patients with high-risk NMIBC³² and limited therapeutic options are available for those with BCG-unresponsive disease after adequate BCG therapy (defined as a minimum of 5 out of 6 doses of an induction course followed by either 2 out of 6 doses of a re-induction course, or 2 of 3 doses of a maintenance course).¹² Patients with BCG-unresponsive disease are unlikely to respond to further BCG therapy, which is associated with an increased risk of progression, and radical cystectomy is therefore the standard and preferred option according to the treatment guidelines.^{13,14} Radical cystectomy is considered curative for some patients, but it is associated with significant morbidity and mortality.¹⁵ The overall 90-day complication rates are up to 28-64%^{16,17} and the majority of early complications following radical cystectomy include gastrointestinal (29%), infection (25%), intestinal obstruction (23%), wound-related complications (15%) and deep vein thrombosis (4.7%); late complications include gastrointestinal bowel obstruction, urinary tract infection, deterioration in renal function, calculi formation, voiding dysfunction and metabolic complications.^{15, 17}

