Cystoscopy with or without Biopsy and Cytology		X			Q12W for 2 years after randomization and Q24W thereafter until recurrence of high-grade disease or disease progression, consent withdrawal, lost to follow-up, or death. Same equipment and methods by the same study staff should be used for the duration of the study whenever possible. Disease assessment will include urine cytology and cystoscopy with or without tumor biopsy according to the modalities described in Section 8.1.1.1 and Section 8.1.1.2.
Patient Reported Outcomes (PROs)					
EORTC-QLQ-C30, EORTC NMIBC24,	X	X	X		All PROs will be completed prior to assessments with the exception of the PTAB, which will be completed immediately after treatment administration. Laboratory assessments may be done prior to PROs if laboratory assessments are done on a date prior to the rest of the study visit. If the EOT and last treatment visits are not on the same day, the PTAB assessment does not need to be completed.
EQ-5D-5L	X	X			
PGIS	X	X			
PGIC	X	X			
TSQ	X				

	EOT*	Post-Treatment Period			*EOT: End of Treatment visit will take place within 7 days of the last dose of PF-06801591 or BCG (whichever is later) or decision to discontinue both drugs. This includes participants that complete the full 25 cycles of treatment as well as participants that discontinue treatment early. **Safety Follow-Up: All participants enter safety follow-up period at EOT. Visits at 30, 60, and 90 days post-EOT. ***Disease Follow-Up: Participants with no recurrence of high-grade disease, disease progression, or persistence of CIS before EOT will be assessed Q12W for 2 years after randomization and Q24W thereafter until recurrence of high-grade disease or disease progression, consent withdrawal, lost to follow-up, or death. Timing of disease assessment is fixed according to the calendar, starting with randomization and should not be adjusted. ****Survival Follow-Up: Q12W until consent withdrawal, lost to follow-up, death, or end of study (5 yrs from last participant randomized). Sponsor may request that sites complete additional survival follow-up to facilitate planned analyses as needed.
		Safety Follow-Up**	Disease Follow-Up***	Survival Follow-Up****	
Visit Window (Days)	+7	±7	±7	±7	
PTAB	X				PROs will be administered in following order: EORTC QLQ-C30, EORTC NMIBC24, EQ-5D-5L, PGIS, PGIC, TSQ, PTAB. See Section 8.1.2.
Survival					

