Subsequent Anti-cancer Therapy	X	X	X	X	Start date and other details of anti-cancer therapy (including cystectomy) subsequent to the study treatment will be recorded.
Survival Follow-up				X	Visit is a phone call Q12W. See Section 8.2.6.
Immunogenicity and Pharmacodynamic Biospecimen					
Pharmacokinetics	X				Collect the last PK sample at EOT. If EOT is done on the same date as the last dose of PF-06801591, all efforts should be made to obtain PK samples within 2 hours prior to PF-06801591 dosing. Arms A and B only. See Section 8.5.
Immunogenicity	X				Collect the last immunogenicity sample at EOT. See Section 8.8.3. Arms A and B only.

AE: adverse event; ADA: anti-drug antibodies; BP: blood pressure; CT: computed tomography, ECG: electrocardiogram, EORTC-QLQ-C30: European Organisation for Research and Treatment of Cancer Quality of Life Questionnaire-30 (items); EOT: end of treatment; MRI: magnetic resonance imaging, NAb: neutralizing antibodies; NMIBC: non-muscle invasive bladder cancer, PGIC: Patient Global Impression of Change; PGIS: Patient Global Impression of Severity; PK: pharmacokinetics, PTAB: Patient Treatment Administration Burden; SAE: serious adverse event; TSQ: Treatment Satisfaction Questionnaire

Screening and Treatment Period – Cohorts B1 and B2

	Screening	Treatment Period	Notes
		Cycles 1-25 (Cohort B1) Cycles 1-17 (Cohort B2)	Cohort B1: Cycle = 4 weeks Cohort B2: Cycle = 6 weeks
	D -28 to D -1	D1	
Visit Window (Days)		±0 (C1) ±7 C2-25 [Cohort B1] C2-C17 [Cohort B2]	
Informed Consent	X	X	Informed consent may be obtained more than 28 days prior to start of study treatment. All screening procedures must be completed within 28 days of registration. The Consent for continuation of treatment at 12 weeks for those participants in Cohort B1 with persistent CIS and Consent for future research will be signed as applicable. Participants must sign consent prior to any trial-specific procedure. See Section 10.1.3.
Tumor and Medical History	X		Detailed information about prior BCG usage, response to prior BCG, and details regarding disease persistence or recurrence will be collected in the CRF. Reasons for subject ineligibility or refusal of radical cystectomy will also be collected. See Section 8 for details.
Physical Examination	X	X	Physical examinations should be performed according to clinical practice. Any abnormalities should be recorded as AEs. See Section 8.2.1.
Weight	X	X	

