All participants will enter the safety follow-up period at EOT. Visits will occur 30 days, 60 days, and 90 days after EOT. Concurrent to the safety follow-up, participants with no recurrence of high-grade disease, progression of disease, or persistence of CIS before EOT, will also continue disease assessment after EOT through the disease follow-up period and will be assessed every 12 weeks for 2 years after randomization and every 24 weeks thereafter until recurrence of high-grade disease or progression of disease, withdrawal of consent for further participation in the study, lost to follow-up, or death.

All participants after recurrence of high-grade disease, persistence of CIS, or progression of disease will be followed via telephone visits every 12 weeks for survival until the earliest of withdrawal of consent for further participation in the study, lost to follow-up, death, study termination by the sponsor, or end of study (5 years from last participant randomized).

The study design for Cohort A is illustrated in [Figure 3](#)

Figure 3. B8011006: Study Schematic Cohort A

*See Section 4.1 for additional details

** For participants with CIS at randomization

CIS: carcinoma in situ, BCG: Bacillus Calmette-Guerin; ROW: rest of world; US: United States

[figure not shown]

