### 6.2.2.10. Time to cystectomy (Cohort A only)

Time to cystectomy is defined as time from 'start date' to cystectomy. Participants without a cystectomy will be censored at death date or last date known to be alive.

The treatment effect will be estimated using a Cox's Proportional Hazard model stratified by randomization strata to calculate the hazard ratio for time to cystectomy between each experimental arm and Arm C.

Kaplan-Meier estimates (product-limit estimates) will be presented by treatment arm together with a summary of associated statistics including the median time to cystectomy with 2-sided 95% CIs. Time to cystectomy rates at 6, 12, 18, 24, 30, 36, 42, and 48 months will be estimated with corresponding 2-sided 95% CIs. The CIs for the median will be calculated according to Brookmeyer and Crowley (1982) and the CIs for the survival function estimates at specific time points will be derived using the log-log transformation according to Kalbfleisch and Prentice (2002) (with back transformation to a CI on the untransformed scale). The estimate of the standard error will be computed using Greenwood's formula. A Kaplan-Meier plot for time to cystectomy will be generated.

Reasons for censoring will be summarized according to the categories in Table 23 following the hierarchy shown.

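### Protocol 8.2.6 and the Cohort A Schedule of Activities disagree on how long cystectomy is recorded, and the SAP's censoring rule would hide any resulting gap

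*Protocol*

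**What the plan says.** Protocol 8.2.6 (Survival Follow-up) states that "any subsequent anti-cancer therapy (including cystectomy), if administered, will be documented and recorded for participants who discontinue the study intervention" and who "continue in post-treatment safety follow-up until recurrence of high-grade disease or progression of disease".

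The Cohort A follow-up table in Protocol 1.3 has a row for subsequent anti-cancer therapy. It is marked at the end-of-treatment visit and in the safety, disease and survival follow-up columns. Its note reads "Start date and other details of anti-cancer therapy (including cystectomy) subsequent to the study treatment will be recorded", with no stop at recurrence or progression. The survival column is defined in the same table: "Survival Follow-Up: Q12W until consent withdrawal, lost to follow-up, death, or end of study (5 yrs from last participant randomized").

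Protocol 4.1.1 says who is in that period: "All participants after recurrence of high-grade disease, persistence of CIS, or progression of disease will be followed via telephone visits every 12 weeks for survival".

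For the endpoint, SAP 3.2.2 measures time from randomization to cystectomy and does not stop the clock at an EFS event. SAP 6.2.2.10 adds: "Participants without a cystectomy will be censored at death date or last date known to be alive". Protocol 9.4.1.1 has a different rule: it censors at the latest date on which the participant was known not to have had the operation.

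**The concern.** Time to cystectomy is a Cohort A secondary objective, and the protocol rationale anticipates fewer later cystectomies with the combination. If treatment lowers that rate by preventing disease failure, the operations after failure carry much of the contrast. In the rationale for Cohorts B1 and B2, the protocol says of BCG-unresponsive disease that "radical cystectomy is therefore the standard and preferred option according to the treatment guidelines". Operations after failure are therefore to be expected in Cohort A as well.

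The stopping point in 8.2.6 falls exactly where that information begins. A participant whose operation goes unrecorded is not missing from the analysis. Under the SAP rule, that participant contributes cystectomy-free follow-up up to the last contact. Cystectomy rates would then be too low in every arm, and a true difference could be weakened or lost. The table of subsequent anti-cancer therapies (SAP 6.5.5), which helps in reading OS, would be cut short in the same way.

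**Working it through.** The documents give no event count, power or alpha for time to cystectomy, so there is no planned figure to reproduce. The check is a comparison of texts, followed by simple arithmetic for scale.

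**1. How long is cystectomy recorded?**

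- Protocol 8.2.6, read plainly: until high-grade recurrence or progression. Persistence of CIS is not named as a stop.
- Schedule of Activities: through survival follow-up to the end of the study.
- Survival follow-up begins at recurrence, persistence of CIS or progression (Protocol 4.1.1). The Schedule therefore requires recording in the period that 8.2.6, read plainly, excludes.

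**2. Is the 8.2.6 limit coherent in itself?** It names safety follow-up, but Protocol 4.1.1 defines that period by three visits: "Visits will occur 30 days, 60 days, and 90 days after EOT". The period that runs until recurrence or progression is disease follow-up. The sentence joins one period's name to another period's end.

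**3. Could a site reach 8.2.6 from the Schedule?** Yes. The Schedule's survival-call row refers the reader to Section 8.2.6, whose stated purpose is to collect OS data and which contains the limiting sentence.

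**4. What does the analysis do with an unrecorded operation?** Take a participant with a high-grade recurrence, a later unrecorded cystectomy, and survival calls that ask only about vital status.

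- Protocol 9.4.1.1: censored when last known to be cystectomy-free, which is about the time of the recurrence.
- SAP 6.2.2.10: censored at death or when last known alive. The nearest SAP definition, date of last contact in 5.3.3.1, counts contacts on the survival follow-up page. Each call therefore adds cystectomy-free time.

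SAP 2.1, which lists departures from the protocol's analysis plan, gives only the two removals of BICR-based complete response analyses. It does not list this censoring change, although the SAP version history records it under version 3.

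The protocol's rule alone would not rescue the estimate. Censoring at recurrence removes participants just as their risk of cystectomy is likely to rise, which is informative. Only recording the operations solves the problem.

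**5. Scale.**

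- Randomized in Cohort A: 1056 (Protocol 4.1.1).
- Expected EFS events at the EFS cut-off, all arms, deaths included: about 261 (Protocol 9.2.1).
- Share: 261 / 1056 = 24.7%.

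This is a rough guide to how many participants reach the disputed period by then. It includes deaths, and it leaves out events censored after two or more missed assessments. If, as a pure assumption, 10% to 50% of them have a cystectomy, then 261 × 0.10 ≈ 26 to 261 × 0.50 ≈ 131 operations would turn on which text was followed. Operations after persistence of CIS alone fall in this count but are not excluded by 8.2.6, so the range describes exposure and not loss.

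**The case against.** The strongest reply is that the protocol already requires what the endpoint needs. The Schedule of Activities marks the item in the survival column and names cystectomy, and Protocol Section 8 treats adherence to the Schedule as essential. The amendment history, used here only as a sign of intent, records one joint change to the Schedule and 8.2.6 reminding sites to record cystectomy after treatment ends. The SAP draws on follow-up surgery pages with no stated stop at an EFS event. All of this stands, and it makes the Schedule the likely intention.

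The 8.2.6 sentence can also be parsed so that its time limit describes how long the participant stays in follow-up and not how long recording lasts. On that reading the section sets no end to recording. The mismatch with the defined safety follow-up period suggests a drafting slip, not a deliberate design. This also stands, but an ambiguous instruction that sites are sent to still needs correcting.

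A reader might go further and infer that time to cystectomy misses most of its events. The documents do not support that. They give no share of cystectomies occurring after failure, and the text on cystectomy as the preferred option concerns BCG-unresponsive patients, not a Cohort A rate. Nothing shows that any site stopped recording. Multiplying an assumed share of late operations by an assumed share of sites following 8.2.6 would give a loss figure with no source for either factor.

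Finally, the SAP reserves the right to modify the protocol's plans, and the endpoint lies outside the alpha-controlled hierarchy. Both are true. They limit the severity but do not remove the contradiction.

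**Conclusion.** Wrong as written: an internal contradiction affecting a secondary endpoint outside the alpha-controlled hierarchy. Protocol 8.2.6, on its plain reading, and the Schedule of Activities give different end points for recording cystectomy and other subsequent therapy. The SAP's censoring rule departs from the protocol's in the direction that turns any gap into apparent cystectomy-free time.

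The conflict and the mechanism are well supported. The size of any loss is not known. It is zero where sites followed the Schedule and completed the follow-up surgery pages. Where sites followed 8.2.6, it covers the cystectomies after high-grade recurrence or progression. The figure of 24.7% shows only how many participants are expected to have an EFS event by the EFS cut-off, and the 26 to 131 range rests on an assumed cystectomy rate. Capture of EFS and OS events is unaffected.

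**What to change.** 1. Amend Protocol 8.2.6 so that subsequent anti-cancer therapy, including cystectomy, is recorded through safety, disease and survival follow-up to the end of the study, in line with the Schedule of Activities.
2. Confirm from sites and the eCRF what was collected after EFS events. At the next scheduled 12-weekly call, ask for the date and type of any cystectomy or other anti-cancer therapy since the EFS event. For participants who have died, obtain this from site records. Enter it on the existing follow-up pages.
3. Change SAP 6.2.2.10 to censor at the date the participant was last known to be free of cystectomy, as in Protocol 9.4.1.1. If the SAP rule is kept, list the departure in SAP 2.1 with its reason.

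The cost is a clarification or amendment line, a one-time query at calls already planned, and modest data entry. No treatment, visit or alpha changes. Randomization ended on 16 November 2021 and calls run for 5 years from then, so they end about November 2026. Missed operations will be harder to recover after that.

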8.2.7. Clinical Safety Laboratory Assessments

- See Section 10.2 for the list of clinical laboratory tests to be performed and to the [SoA](#) for the timing and frequency. Specimen for laboratory assessments may also be drawn when clinically indicated.
- Repeat samples do not have to be drawn on C1D1 if the samples were drawn in the prior 7 days. Laboratory tests may be performed up to 3 days prior to the scheduled clinic visit including the C1D1 visit, so that results will be available for review before study treatment administration.
 - Assessments and physician's evaluation of the following labs, at a minimum, must be performed prior to dosing at visits per Section 1.3, Schedule of Activities:
 - Pregnancy test (as applicable)
 - Hematology (per Section 6.6.1)
 - Liver function: AST, ALT, and bilirubin (per Section 10.13)
 - Renal function: Creatinine (per Section 10.13)
 - Any other per protocol lab test(s) that correlate to clinical signs or symptoms
 - Results from pregnancy tests, if taken, must be available for review prior to dosing.
 - Laboratory assessments will be collected per [SoA](#).
 - Laboratory assessments must be performed, and results reviewed by the treating physician as soon as they are available.
 - The investigator must review the laboratory report, document this review, and record any clinically relevant changes occurring during the study in the AE section of the eCRF. The laboratory reports must be filed with the source documents. Clinically significant abnormal laboratory findings are those which are not associated with the underlying disease, unless judged by the investigator to be more severe than expected for the participant's condition.

- All laboratory tests with values considered clinically significantly abnormal during participation in the study or within AE/SAE reporting criteria after the last dose of study treatment should be repeated until the values return to normal or baseline or are no longer considered clinically significant by the investigator or medical monitor.
 - If such values do not return to normal/baseline within a period of time judged reasonable by the investigator, the etiology should be identified, and the sponsor notified.
 - All protocol-required laboratory assessments, as defined in Section 10.2, must be conducted in accordance with the [SoA](#).
 - If laboratory values from non-protocol specified laboratory assessments performed at the institution's local laboratory require a change in participant management or are considered clinically significant by the investigator (eg, SAE or AE or dose modification), then the results must be recorded in the eCRF.

8.2.8. Pregnancy Testing

Pregnancy tests may be urine or serum tests but must have a sensitivity of at least 25mIU/mL.

Pregnancy tests will be performed in WOCBP at the times listed in the [SoA](#). Following a negative pregnancy test result at screening, appropriate contraception must be commenced and a second negative pregnancy test result will be required at the baseline visit prior to the participant's receiving the study intervention. Pregnancy tests will also be done whenever 1 menstrual cycle is missed during the active treatment period (or when potential pregnancy is otherwise suspected) and at the end of the study. Pregnancy tests may also be repeated if requested by IRBs/ ECs or if required by local regulations. If a urine test cannot be confirmed as negative (eg, an ambiguous result), a serum pregnancy test is required. In such cases, the participant must be excluded if the serum pregnancy result is positive.

8.3. Adverse Events and Serious Adverse Events

The definitions of an AE and an SAE can be found in Section 10.3.

The definitions of device-related safety events (ADEs and SADEs) can be found in Section 10.7. Device deficiencies are covered in Section 8.3.9.

AEs will be reported by the participant (or, when appropriate, by a caregiver, surrogate, or the participant's legally authorized representative).

The investigator and any qualified designees are responsible for detecting, documenting, and recording events that meet the definition of an AE or SAE and remain responsible to pursue and obtain adequate information both to determine the outcome and to assess whether it meets the criteria for classification as an SAE, or that caused the participant to discontinue the study intervention (see Section 7.1).

Each participant will be questioned about the occurrence of AEs in a nonleading manner.

In addition, the investigator may be requested by Pfizer Safety to obtain specific follow-up information in an expedited fashion.

